#### **7.7.4 7-point clinical status ordinal scale:**

The ordinal scale is an assessment of the clinical status at a given study day:

1. Limitation of activities
2. Hospitalized, no oxygen therapy
3. Oxygen by mask or nasal prongs
4. Non-invasive ventilation or high-flow oxygen
5. Intubation and mechanical ventilation
6. Ventilation+ additional organ support (vasopressor, RRT, ECMO)
7. Death

#### **7.7.5 Sequential Organ Failure Assessment (SOFA) score:**

The Sequential Organ Failure Assessment (SOFA) is a morbidity severity score and mortality estimation tool developed from a large sample of ICU patients throughout the world. The SOFA was designed to focus on organ dysfunction and morbidity, with less of an emphasis on mortality prediction. It requires the following (worst value within past 24 hours):

- $\text{FiO}_2$
- $\text{PaO}_2$
- Mechanical ventilation y/n
- Platelets
- Bilirubin
- Glasgow coma scale
- Mean arterial pressure
- Vasopressors y/n
- Creatinine
- Urine output

This can be calculated by entering the results above into an online tool:

<https://clincalc.com/IcuMortality/SOFA.aspx>

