## 7.5 Visit schedule and assessments post initiation of treatment

### 7.5.1 Cohort 1 and 2

Any assessments that are done as per routine care do not need to be repeated.

- Documentation of respiratory status: Respiratory status of patients is monitored hourly and data points will be extracted for every four hours where available until 5 days after the last dose for cohort 1, but one data point per day is required as a minimum. For cohort 2 data will be extracted once a day coinciding with the worst PF ratio. As PF ratio is the primary endpoint, in addition to the worst PF ratio over the preceding 24 hrs up to a maximum of 6 data points spread across 24 hrs that represents patients clinical status will be extracted. Similar to cohort 1 respiratory data will be collected until 5 days after the last dose. After this period, respiratory status is to be documented weekly (+/- 1 day) until discharge, death, or 28 days whichever occurs first. The time of measurement should be documented.
- The variables include:
  - Details of oxygen and respiratory support including the type of device, FiO2 Respiratory rate
  - PaO2
  - For IMV patients, details of ventilation including but not exclusively the below
    - Tidal volume (in mL)
    - Full sedation or not – not for cohort 2
    - Paralysis or not – not for cohort 2.
    - Patient position – not for cohort 2
    - Peak inspiratory pressure (collected for computing compliance)
    - PEEP (collected for computing compliance)
  - For non-invasive oxygen support patients:
    - National Early Warning Score (NEWS 2) – not for cohort 2
    - Oxygen flow rate
    - SpO2
  - For CPAP patients
    - Positive end expiry pressure (PEEP)

The following tests are to be done at a minimum once a day until 5 days after the last dose (day 7 for SOC patients) in cohort 1, a minimum every other day in cohort 2, and then as required until day 28, discharge or death whichever occurs first.

- Local blood testing as per section 7.6.2

The following tests will be done once at 48 h (+/- 24 h) and 96 h (+/- 24h) after start of treatment and then twice weekly while on treatment until 5 days after stopping treatment. After this period, testing should be weekly (+/- 1 day) until day 28, discharge or death whichever occurs first. Twice weekly testing should be evenly spaced across weekdays if possible.

- Research blood sampling as per section 7.6.2

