## 10.2 Secondary endpoints

1. Changes in lung compliance (defined as tidal volume / (peak inspiratory pressure – PEEP)) from baseline and absolute values at day 5 (96 hrs  $\pm 2$  hrs), day 7 (144 hrs  $\pm 4$  hrs), end of treatment, 3 and 5 days post end of treatment

2. Clinical status as assessed by a 7-point WHO ordinal scale at baseline and daily up to 5 days post end of treatment and at day 28, discharge or death (whichever comes first).
3. Mean daily Sequential Organ Failure Assessment (SOFA) score at baseline through to 5 days post end of treatment
4. In follow up period, number of oxygenation free days, ventilator free days, intensive care stay, up to 28 days or death or discharge, whichever occurs first.
5. Incidence and number of days of new oxygen use, non-invasive ventilation or high flow oxygen devices in the first 28 days.
6. Incidence and number of days of new mechanical ventilation use during in the first 28 days
7. In hospital mortality

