6.4 Analysis of secondary outcomes

All secondary outcomes will be summarized by group. Categorical variables shall be reported as frequencies and percentages. Reports of continuous variables shall include mean or median and standard deviation or interquartile range (IQR) as appropriate, as well as minimum and maximum values.

In addition, we will make use of the daily measurements of clinical status, measurements of lung compliance, NEWS 2 and SOFA score, summarising them at each post baseline timepoint by group. The evolution of these outcomes over time will also be summarised graphically.

7 Software

The statisticians will download the data from the trial specific database into a format suitable to be read by Stata. All the statistical analysis will be performed using Stata version 15 (or above) and/or R version 4.0.2 (or above).

8 References

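### The SOFA rule takes the worst PaO2 and worst FiO2 of the day separately and sets no same-time rule, so read literally the respiratory item can rest on a P/F ratio that never occurred

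*Protocol*

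**What the plan says.** Protocol section 7.7.5 opens the list of SOFA inputs with "It requires the following (worst value within past 24 hours". FiO2 and PaO2 are separate entries and the P/F ratio is not an entry. The score is then obtained as follows: "This can be calculated by entering the results above into an online tool". No same-time requirement is stated there or elsewhere.

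SOFA is a secondary endpoint: "Mean daily Sequential Organ Failure Assessment (SOFA) score at baseline through to 5 days post end of treatment" (Protocol section 10.2). Protocol section 10.6.3 also summarises its change from baseline. SAP section 6.4 will use "measurements of lung compliance, NEWS 2 and SOFA score, summarising them at each post baseline timepoint by group", with no derivation of SOFA and no test on it.

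The number of readings available each day is not fixed:

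- **Cohort 1, treated** (Protocol section 7.5.1): "Respiratory status of patients is monitored hourly and data points will be extracted for every four hours where available", "but one data point per day is required as a minimum".
- **Cohort 2** (same section): one daily extraction at the worst P/F and, "in addition to the worst PF ratio over the preceding 24 hrs up to a maximum of 6 data points spread across 24 hrs".
- **Historical controls** (Protocol section 7.5.2): PaO2, FiO2 and SOFA are collected where available, with no stated frequency.

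For the primary endpoint, Protocol section 10.6.2 makes P/F a field calculated in the database from PaO2 and FiO2. Nothing links that field to SOFA.

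**The concern.** FiO2 can be adjusted during the day, so the lowest PaO2 and the highest FiO2 may belong to different blood gases. Someone following section 7.7.5 to the letter would enter both extremes, and the tool would score a ratio that the patient never had. The same patient-day could then carry one worst P/F for the primary endpoint and a lower one inside SOFA.

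The error has one direction and depends on how many readings are available. It therefore need not cancel where reading frequency differs: between a patient's baseline and later days, or between cohort 1 treated patients and controls taken from routine notes.

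**Working it through.** The documents give no SOFA figure to reproduce, so the check has three parts.

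**1. Direction.** Let the day's readings be pairs (P_j, F_j), j = 1 to k. For any reading m, min(P) ≤ P_m and max(F) ≥ F_m, so min(P)/max(F) ≤ P_m/F_m. This holds for every m, hence

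min(P)/max(F) ≤ min(P/F).

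The two sides are equal when k = 1, when FiO2 does not change, or when one reading holds both extremes. Otherwise the separate-items ratio is strictly lower.

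**2. Example** (illustrative values):

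- Reading A: 60/0.40 = 150.
- Reading B: 90/0.80 = 112.5.
- Worst P/F that occurred: 112.5.
- Separate items: 60/0.80 = 75.
- Shortfall: (112.5 − 75)/112.5 = 33%.

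The documents do not give the SOFA cut-points. If the item steps at 400, 300, 200 and 100 mmHg, the last two on ventilation (assumption), a ventilated patient moves from 3 to 4.

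**3. Average size.** Four-hourly extraction gives at most 24/4 = 6 readings a day. The variability of PaO2 and FiO2 within a day is not in the documents, so three sets of assumptions were simulated:

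- **Model A.** True P/F uniform on 80 to 300; within-day log-scale SD of P/F 0.10 to 0.20; PaO2 centred at 70 mmHg with log-scale SD 0.10 to 0.15; FiO2 = PaO2/(P/F), limited to 0.21 to 1.0 and redrawn at every reading.
- **Model B.** PaO2 and FiO2 log-normal around 80/0.5, 80/0.7 and 85/0.35; log-scale SD 0.10 to 0.20; correlation −0.5 to 0.5.
- **Model C.** FiO2 stays put between readings except for a 10% to 25% chance of change; log-scale SD 0.15 for FiO2 and 0.12 for PaO2.

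| Model | Mean P/F shortfall, 2 readings | Mean P/F shortfall, 6 readings |
|---|---|---|
| A | 6% to 11% | 14% to 24% |
| B | 1.5% to 10% | 3.4% to 22% |
| C | 0.4% to 1% | 2% to 4% |

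At one reading a day, or with constant FiO2, the shortfall is 0%.

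On the assumed 100 mmHg steps, at six readings the item changes on 23% to 45% of days in model A and on 3% to 7% in model C. In model B the mean excess is about 0 to 0.26 points at two readings and 0 to 0.6 at six.

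The P/F shortfall grows with the number of readings whenever FiO2 varies. The excess in points need not, because of score bands and the ceiling: one model B setting (80/0.7, SD 0.10, correlation 0.5) gives 0.22 points at 2 readings, 0.50 at 6 and 0.10 at 24.

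**What pairing leaves behind.** A correctly paired daily worst also falls as readings increase. In model A, going from 2 to 6 readings lowers the paired worst P/F by 7% to 13% and raises the item by 0.11 to 0.24 points, against 0.28 to 0.40 points unpaired. About one third to two thirds of the frequency effect therefore remains after pairing.

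**The case against.** The strongest reply is that section 7.7.5 is shorthand. Its list includes yes/no entries for ventilation and vasopressors, so the parenthesis may mean only a 24-hour window, and staff may pair the values without being told. That is possible, but the text does not ask for it, and a score entered by hand in an outside tool needs the rule written down.

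The size is also open to challenge. Model A redraws FiO2 at every reading, which exaggerates the mismatch; where FiO2 rarely changes, the effect is small. This stands, and the range is wide for that reason.

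A reader might infer three stronger points that the documents do not support:

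- **Bias between cohort 1 and cohort 2.** Protocol section 10.6 analyses the cohorts separately, so no planned comparison is affected. Cohort 2's daily extraction is already tied to the worst P/F, though not linked to SOFA, and its separate SAP is not among the documents.
- **Sparser sampling that looks like organ recovery.** Only SAP section 5.5 describes a move from four-hourly to daily readings after the first week. Protocol section 7.5.1 and the footnote to the SAP's own schedule keep four-hourly extraction until 5 days after the last dose, which is also when daily SOFA ends for treated patients.
- **Scores already wrong.** No document shows that unpaired values were entered.

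**Conclusion.** The concern holds as a gap in the derivation rule. Section 7.7.5, read literally, gives a ratio that is never above and can be below the worst P/F that occurred, so it can only raise the respiratory item. The direction is arithmetic and needs no assumption. The size, roughly 2% to 24% lower P/F at six readings a day, rests wholly on assumed within-day variability and would be nil where FiO2 is constant.

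The consequence is limited: one SOFA item, in a secondary endpoint that is only summarised, in a pilot whose analyses are declared hypothesis generating. It matters chiefly for change from baseline within a group, and for the descriptive comparison of the 9 treated cohort 1 patients with 18 historical controls whose reading frequency is not fixed. The correction is worth making because it is cheap.

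**What to change.** 1. In Protocol section 7.7.5 and in the SAP, replace the separate FiO2 and PaO2 inputs with one: the PaO2 and FiO2 recorded at the same time point that give the lowest PaO2/FiO2 in the past 24 hours.
2. Derive the respiratory item from the P/F field that section 10.6.2 already has the database calculate, in all groups.
3. Check how cohort 1 and control scores were obtained, and recompute only those found to use unpaired values.
4. Report the number of readings per day by group beside the SOFA summaries, since pairing does not remove the whole dependence on reading frequency.

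The cost is one sentence in each document, a database derivation and a check of existing scores. Section 7.5.1 already asks for measurement times in treated patients. Section 7.5.2 does not mention them for controls, so some may have to be taken from the records.

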#### **7.7.6 Glasgow Coma Scale:**

The Glasgow coma scale is used to assess patients in a coma. The initial score correlates with the severity of brain injury and prognosis. The Glasgow Coma Scale provides a score in the range 3-15; patients with scores of 3-8 are usually said to be in a coma.

Scoring is done according to the table below:

	1	2	3	4	5	6
Eye	Does not open eyes	Opens eyes in response to pain	Opens eyes in response to voice	Opens eyes spontaneously	N/A	N/A
Verbal	Makes no sounds	Makes sounds	Words	Confused, disoriented	Oriented, converses normally	N/A
Motor	Makes no movements	Extension to painful stimuli (decerebrate response)	Abnormal flexion to painful stimuli (decorticate response)	Flexion / Withdrawal to painful stimuli	Localizes to painful stimuli	Obeys commands

Maximum score is 15 which has the best prognosis

Minimum score is 3 which has the worst prognosis

Scores of 8 or above have a good chance for recovery

Scores of 3-5 are potentially fatal, especially if accompanied by fixed pupils or absent oculovestibular responses.

### 7.7.7 National Early Warning Score (NEWS - 2)

The NEWS, like many existing Early Warning Score systems, is based on a simple scoring system in which a number is allocated to physiological measurements (Vital Signs) already routinely measured in hospital and recorded on the patient clinical chart. The six simple physiological parameters form the basis of the scoring system:

1. Respiratory rate
2. Oxygen saturations
3. Temperature
4. Systolic blood pressure
5. Heart rate
6. Level of consciousness.

Values are added to each variable using the table below:

Physiological Parameters	3	2	1	0	1	2	3
Respiration Rate (BPM)	≤8		9-11	12-20		21-24	≥25
Oxygen Saturations (%)	≤91	92-93	94-95	≥96			
Any Supplemental Oxygen		Yes		No			
Temperature (°C)	≤35		35.1-36.0	36.1-38.0	38.1-39.0	≥39.1	
Systolic Blood Pressure (mmHg)	≤90	19-100	101-110	111-219			≥220
Heart Rate (BPM)	≤40		41-50	51-90	91-110	111-130	≥131
Level of Consciousness				A			V, P or U

Clinical risk is assigned based on the total score:

- Aggregate score 1-4: Low
- Aggregate score 5-6: Medium
- Aggregate score 7 or more: High

Refer to <https://www.activ8rlives.com/support/data-collected/cardiovascular-and-respiratory/national-early-warning-score-news/>

## 7.8 Discontinuation/withdrawal of participants

In consenting to participate in the trial, participants or legal representatives on their behalf are consenting to trial treatment, assessments, follow-up and data collection.

### 7.8.1 Discontinuation of Trial Treatment for clinical reasons

A participant may be withdrawn from trial treatment whenever continued participation is no longer in the participant's best interests, but the reasons for doing so must be recorded.

The decision to withdraw a participant from treatment must be recorded in the CRF and medical notes, and the sponsor when required should be notified in writing.

### 7.8.2 Participant withdrawal from trial treatment and/or follow-up

If a participant expresses their wish to withdraw from trial treatment or trial follow-up, sites should explain the importance of remaining on trial follow-up and seek permission to allow use of routine follow-up data to be used for trial purposes. The importance of safety follow-up should be emphasised to the participant in the Participant Information Sheet.

The decision of the participant to withdraw from treatment or follow-up must be recorded in the CRF and medical notes.

The participant may withhold their reason for withdrawal however, if the participant gives a reason for their withdrawal, this should be recorded.

### 7.8.3 Withdrawal of Consent to Data Collection

If a participant explicitly states, they do not wish to contribute further data to the trial their decision must be respected and recorded in the CRF and medical notes.

## 7.9 Replacements

Replacement of withdrawn patients may occur at the discretion of the Investigator.

## 7.10 Stopping rules

The trial may be stopped before completion for the following reasons:

- On the recommendation of the sponsor and CI
- A major pulmonary bleeding that is symptomatic or fatal that occurs between start of treatment and 30 hours after the last dose.
- Cohort 1 - A 50% or greater reduction of fibrinogen at 72 hrs (from baseline value at screening) in either of the first 2 patients after dosing. If we see a 50% or greater drop in fibrinogen in a patient, it would only be a particular safety concern in that patient if the fibrinogen were to go below 1.5 g/L (hence why this level is stated as a reason to stop dosing in an individual patient). However, if we do see a 50% drop in fibrinogen from baseline values in either of the first 2 patients it might suggest that the dose is too high overall with secondary systemic absorption. As such stopping the trial will provide us the opportunity to discuss within the TMG and IDMC to make a decision on the dose going forward. A substantial amendment would be made to the MHRA and REC.
- Any fatal bleeding that occurs between start of treatment and 30 hours after the last dose.
- Symptomatic bleeding in a critical area or organ, such as intracranial, intraspinal, pericardial, pulmonary or intramuscular with compartment syndrome, that occurs between start of treatment and 30 hours after the last dose.

Further enrolment into the study will be put on hold in the event of any of the stopping rules and a substantial amendment will be submitted to temporarily halt the trial. Whenever the study is stopped in addition to a review of the data by the trial management group consisting of the investigators, the DMC will also be convened for review of the data to assess the risk benefit of progressing the pilot study. If, following an internal safety review by the DMC, the Sponsor deems it appropriate to restart the trial; this can only be done following approval by the MHRA and REC and along with any local approvals required.

## 7.11 Definition of End of Trial

The end of trial is the date of discharge, death, or day 28 of the last patient whichever is sooner.

## 8 Recording and reporting of adverse events and reactions

Collection, recording and reporting of adverse events (including serious and non-serious events and reactions) to the sponsor will be completed according to the sponsor's SOP (INV/S05).

## 8.1 Definitions

Term	Definition
Adverse Event (AE)	
Any untoward medical occurrence in a patient or clinical trial participant administered a medicinal product and which does not necessarily have a causal relationship with this treatment. Therefore an AE can be any unfavourable or unintended change in the structure (signs), function (symptoms) or chemistry (laboratory data) in a participant to whom an IMP or procedural intervention has been administered, including occurrences which are not necessarily caused by or related to that product.

Adverse Reaction (AR)	
Any untoward and unintended response in a participant to an investigational medicinal product which is related to any dose administered to that participant.
 
This includes medication errors, uses outside of protocol (including misuse and abuse of product)

Serious Adverse Event (SAE), Serious Adverse Reaction (SAR) or Unexpected Serious Adverse Reaction	
Any adverse event, adverse reaction or unexpected adverse reaction, respectively, that:
 
 
• results in death,
 
• is life-threatening*,
 
• requires hospitalisation or prolongation of existing hospitalisation**,
 
• results in persistent or significant disability or incapacity, or
 
• consists of a congenital anomaly or birth defect
 
 
*A life-threatening event, this refers to an event in which the participant was at risk of death at the time of the event; it does not refer to an event which hypothetically might have caused death if it were more severe.
 
** Hospitalisation is defined as an in-patient admission, regardless of length of stay. Hospitalisation for pre-existing conditions, including elective procedures do not constitute an SAE.
 
Some medical events may jeopardise the subject or may require an intervention to prevent one of the above characteristics/consequences. Such important medical events should also be considered as serious.
 
The term “severe” is often used to describe the intensity of an event or reaction (e.g. mild, moderate or severe) and should not be confused or interchanged with the term “serious”.

Suspected Unexpected Serious Adverse Reaction (SUSAR)	A serious adverse reaction, the nature, severity or outcome of which is not consistent with the Reference Safety Information.
Reference Safety Information (RSI)	A list of medical events that defines which reactions are expected for the IMP being administered to clinical trial subjects, and so do not require expedited reporting to the Competent Authority. It is contained in a specific section in the Summary of product characteristics (SmPC) or the Investigator Brochure (IB).

## 8.2 Recording adverse events

All adverse events will be recorded in the medical records in the first instance. Non-serious AEs will not be collected in the CRFs for this trial, apart from the adverse events of special interest (AESI) listed below:

- Bleeding events

In addition, any Serious Adverse Events (SAEs) assessed as likely to be related to IMP administration will be collected. See section 8.4 for further details on recording and reporting of Serious Adverse Reactions (SARs). These AESIs and Serious Adverse Reactions (SARs) will be recorded with clinical symptoms and accompanied with a simple, brief description of the event, including dates as appropriate, until the participant completes the trial.

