The table below summarises the risks, frequencies and mitigations of the IMP(s) and NIMP(s):

Name of IMP(s)	Potential risk	Risk Frequency	Risk Management
rtPA (alteplase)	Pulmonary haemorrhage	Uncommon when administered intravenously, unknown when administered by ventilation	Stop rtPA nebulisation for this patient, and administer fibrinogen concentrate or cryoprecipitate if fibrinogen is < 1.0 g/L, and other supportive treatment including IV tranexamic acid. May trigger stopping rule for trial if considered a

			major bleed by ISTH criteria (see section 7.10)
rtPA (alteplase)	Minor bleeding particularly traumatic – suction through endotracheal tube or at site of venepuncture	Common when administered intravenously, unknown when administered by ventilation	Supportive treatment, and use caution during suction
rtPA (alteplase)	hypersensitivity reactions (e.g. rash, urticaria, bronchospasm, angio-oedema, hypotension, shock)*	Rare when administered intravenously, unknown when administered by ventilation	Anti- allergic medications
rtPA (alteplase)	serious anaphylaxis	very rare when administered intravenously, unknown when administered by ventilation	Treat per local protocols and stop further administration of rtPA for this patient.
rtPA (alteplase)	Major Bleeding including intracerebral haemorrhage	Common when administered intravenously, unknown when administered by ventilation.	Rapid absorption is required to achieve high enough levels to result in bleeding. the plasma half-life is 5 minutes.  Stop rtPA nebulisation for that patient, and administer fibrinogen concentrate or cryoprecipitate if fibrinogen is < 1.0 g/L. May trigger stopping rule for trial (see section 7.10)

The table below summarise the risks and mitigations of all test above standard care that are being performed in a table:

Intervention	Potential risk	Risk Management
Additional blood samples	Related to venepuncture, which is done as standard of care.	Press on the site of blood tests

## 2.7 Safety data from cohort 1

Preliminary data from the 9 treatment arm patients is summarised below (this data is preliminary data and is not the final analysis):

All bleed events were identified as adverse events of special interest and evaluated for severity (mild, moderate and severe as described in section 8.3.1) and causality. In addition, the ISTH (International Society of Haemostasis and Thrombosis) classification for bleed severity as used for anticoagulation studies was implemented.

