## 3 Objectives

### 3.1 Primary Objectives

1. Efficacy: Investigate the potential for efficacy of nebulised rtPA in patients presenting with severe COVID-19 requiring IMV or non invasive support with NIV OR continuous positive airway pressure (CPAP) OR high flow oxygen OR standard oxygen therapy
2. Safety: Evaluate the safety of nebulised rtPA treatment.

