### 5.2 Source of IMP, Manufacture, Distribution and Storage

Actilyse will be supplied from existing hospital stock and replenished as required free-of-charge directly to the pharmacy by the manufacturer (Boehringer Ingelheim Ltd).

In this study Actilyse will be administered by nebulisation rather than intravenous injection. The rationale for selecting this route of administration is described in section 3.3.

A proof-of-concept nebulisation study (personal communication from [name], Boehringer Ingelheim) indicated that at the planned concentration of 2 mg/mL nebulisation produces a fine particle fraction of approximately 60%. This means that, in principle, 60% of the dose is able to reach the deep lungs.

The potential irritant effect of nebulised rtPA (with excipients: arginine, phosphoric acid for pH-adjustment, polysorbate 80) on the lungs is not known, but experience within the critical care setting indicates that risk will be low and manageable.

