## 8.4 Procedures for recording and reporting Serious Adverse Reactions

All SAEs will be recorded in the medical records in the first instance. Only serious adverse events assessed as likely to be related to IMP administration, Serious Adverse Reactions (SARs), will be recorded in the CRF, and the sponsor's SAE log. The SAE log will be reported to the sponsor at the end of the study.

SARs will be recorded from the start of treatment until the end of the study.

All SARs must be recorded on a SAE Reporting Form. The CI/PI or designated individual will complete the sponsor's SAE form and email to the Sponsor at [contact] immediately and no later than 24 hours of his / her becoming aware of the event. The Chief or Principal Investigator will respond to any SAE queries raised by the sponsor as soon as possible.

Completed SAE forms must be sent within 24 hours of becoming aware of the event to the Sponsor

Email forms to [contact]

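### Bleeding is the only non-serious adverse event collected, so non-serious hypersensitivity, bronchospasm and airway irritation from nebulised rtPA will be neither collected nor summarised

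*Protocol*

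**What the plan says.** Protocol section 8.2 sets the collection rule in three steps:

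- **Source record:** "All adverse events will be recorded in the medical records in the first instance".
- **Non-serious events:** "Non-serious AEs will not be collected in the CRFs for this trial, apart from the adverse events of special interest (AESI) listed below". The single item listed is bleeding events.
- **Serious events:** "any Serious Adverse Events (SAEs) assessed as likely to be related to IMP administration will be collected". Section 8.4 repeats the restriction: "Only serious adverse events assessed as likely to be related to IMP administration, Serious Adverse Reactions (SARs), will be recorded in the CRF".

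The protocol also names risks that this rule leaves out. The risk table in section 2.6 lists hypersensitivity, with bronchospasm and angio-oedema among its examples, and gives its frequency as "Rare when administered intravenously, unknown when administered by ventilation". Section 5.2 says "The potential irritant effect of nebulised rtPA (with excipients: arginine, phosphoric acid for pH-adjustment, polysorbate 80) on the lungs is not known", and the same sentence goes on to expect the risk to be low and manageable on the basis of critical care experience. Section 5.5 notes that ACE inhibitors may raise the risk of hypersensitivity.

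The primary safety objective in section 3.1 is general: "Safety: Evaluate the safety of nebulised rtPA treatment". The three primary safety endpoints (section 10.1.2) are major bleeding attributable to the drug, low fibrinogen, and serious adverse events causally related to treatment. SAP section 6.3 summarises bleeding, fibrinogen and serious adverse events, and nothing else on safety.

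**The concern.** The nebulised route is the new element of this trial. Local airway reactions and hypersensitivity are the harms on which the protocol admits it has no frequency data by that route. The collection rule is built around systemic bleeding, so the milder forms of these reactions fall outside it.

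Cohort 2 makes this matter more. Each nebulisation is 20 mg rather than 10 mg (section 5.3), and the exclusion for severe cardiopulmonary disease in section 6.1.2 does not appear in the cohort 2 list (section 6.1.4). Section 12.2 asks the DMC to advise on progression to a randomised trial from the safety and efficacy data collected. Tolerability of repeated nebulisation is part of what that advice needs, and its non-serious part would be missing.

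**Working it through.** The documents give no rate for these events, and section 10.4.1 says the sample size has no statistical basis. There is therefore no planned figure to reproduce. The check is mainly a reading of the text, with an illustration of scale.

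**Step 1. Follow each type of case through the plan.**

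| Case | In the CRF as an event? | In a planned summary? |
|---|---|---|
| Bleeding, any seriousness | Yes (8.2) | Yes (10.6.2; SAP 6.3) |
| Hypersensitivity or airway reaction, serious, judged likely related | Yes (8.2, 8.4) | Yes, endpoint 3 (10.1.2) |
| Same, serious, not judged related | No (8.4) | No source in the CRF |
| Same, non-serious | No (8.2) | No |

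Section 10.6 promises a separate SAP for cohort 2, but that SAP cannot tabulate events that the CRF does not hold.

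**Step 2. Ask whether treated reactions become serious.** Section 8.1 widens seriousness to important medical events: "Some medical events may jeopardise the subject or may require an intervention to prevent one of the above characteristics/consequences". This brings in some treated reactions. However, section 8.3.1 grades as moderate an event that needs intervention without damaging health, so a bronchospasm that is treated and resolves can remain non-serious.

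**Step 3. Illustrate the scale.** Inputs: n = 30 (cohort 2, section 4.1), and an assumed per-patient rate p, the same and independent across patients.

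Chance that at least one patient is affected = 1 − (1 − p)^30:

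- p = 1%: 1 − 0.99^30 = 26.0%
- p = 5%: 1 − 0.95^30 = 78.5%
- p = 10%: 1 − 0.90^30 = 95.8%

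If the events were collected and none occurred, the one-sided 95% upper bound would be 1 − 0.05^(1/30) = 9.5%. Under the two-sided convention of SAP section 6.1, the exact 95% upper limit would be 1 − 0.025^(1/30) = 11.6%. For non-serious cases the current rule gives neither a count nor a bound.

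**Step 4. Ask how much the serious-and-related route recovers.** Let q be the assumed share of cases that are both serious and judged likely related. With p = 10%, the chance of at least one recorded case is 1 − (1 − 0.10q)^30:

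| q | Chance of at least one recorded |
|---|---|
| 0 | 0% |
| 0.10 | 26.0% |
| 0.25 | 53.2% |
| 0.50 | 78.5% |
| 1 | 95.8% |

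Capture of these event types as a whole is reduced by an amount that depends on q. Capture of the non-serious ones is nil at any true rate.

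**The case against.** The best defence is that the plan has several other ways of seeing these reactions, and that lean collection is reasonable in a pandemic pilot.

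- **Serious cases are covered.** Any serious event judged likely related enters the CRF, counts under the third safety endpoint, and is reported as a SUSAR (section 8.3.3). In patients with PaO2/FiO2 of 300 or less, a marked bronchospasm or angio-oedema could well qualify. This stands. A reader might infer that these reactions cannot appear in the safety results at all; the documents do not support that.
- **Respiratory data are extracted.** Section 7.5.1 takes, for cohort 2, the worst ratio of each day plus up to six further points, with measurement times. It also takes SpO2 in non-invasive patients, and tidal volume, peak pressure and PEEP in ventilated patients. A desaturation may therefore be in the data. What is missing is an event label and a link to a dose.
- **Indirect traces exist.** Concomitant medication is reviewed daily (7.5.1). Withdrawal from treatment is recorded with reasons (7.8.1), and discontinuations are tabulated with reasons (10.6.1). These help only in part. A medication entry need not show why the drug was given. The hypersensitivity row in section 2.6 lists anti-allergic treatment without mentioning discontinuation, so a reaction need not produce a withdrawal.
- **The irritancy risk was considered.** Section 5.2 expects it to be low and manageable. That is an expectation, and collecting the events is how the trial could confirm it.

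A reader might also infer that the plan would report a zero rate of such reactions. It would not: it makes no report on them, which is a gap and not a false result.

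**Conclusion.** The point holds for non-serious, non-bleeding reactions. Bleeding is the only non-serious event collected, so non-serious hypersensitivity, bronchospasm and airway irritation will not be summarised in either cohort, although safety is a primary objective and the protocol calls the first two unknown in frequency and the third not known by this route. Serious cases are captured, but only through a judgement of relatedness that is hard to make when the underlying disease is ARDS.

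The reading of the text needs no assumption. The size does: the 26%, 79% and 96% rest on assumed rates of 1%, 5% and 10% in 30 independent patients, and nothing in the documents favours one of these rates over another. The bound of 9.5% supposes full collection in all 30 and no cases. This is an inexpensive improvement to safety reporting that should be made; it does not undermine the bleeding or fibrinogen endpoints.

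**What to change.** In section 8.2, add one item to the AESI list: hypersensitivity or bronchospasm/airway reaction of any grade, including any reaction that interrupts a nebulisation, with time of onset relative to the last dose. In the cohort 2 SAP and the DMC tables, report patients affected as n/N with an exact 95% confidence interval, overall and by ventilation group.

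A broader AESI for acute respiratory deterioration around a dose is optional. Desaturation and pressure rises are expected in ARDS, cohort 2 has no control group, and counts could not be attributed to the drug. It would also need a time window defined in advance.

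The cost is slightly more data entry and a protocol amendment during a recruitment period expected to last 2 to 6 weeks (section 10.4.1). Adverse events are already reviewed daily during treatment and for 5 days after the last dose (7.5.1), and each is already to be assessed for severity, causality and seriousness (8.3). The added work is therefore mainly transcription and the onset time. The change concerns data collection only.
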